6 HANDLING OF MISSING VALUES

No imputation for missing values will be performed.

7 STATISTICAL METHODOLOGY AND STATISTICAL ANALYSES

All analyses described in this section will be conducted using the FAS.

7.1 STATISTICAL METHODS

Continuous variables will be summarized using the number of patients, mean, standard deviation (SD), interquartile range (IQR), minimum, median and maximum. Categorical variables will be summarized using the frequency and percentage. Time-to-event endpoint will be summarized using the Kaplan-Meier method. A confidence interval (CI) of a specific percentile will be derived by the Brookmeyer and Crowley method. A CI of survival probability will be estimated using Greenwood's formula. Cox proportional hazards model may be performed to examine the association between time-to-event endpoint and covariates if data allows.

7.2 STATISTICAL ANALYSES

7.2.1 Time to Treatment Failure

TTF will be summarized using the Kaplan-Meier method with the Kaplan-Meier plot. Percentiles of survival curve (25%, median and 75%) with their 2-sided 95% CIs will be estimated. Yearly rates with their 2-sided 95% CI will also be provided. If patients

continue a treatment at the date of data entry, TTF will be censored at the available last date of treatment or the study end period.

TTF will be evaluated by each treatment below:

- TTF of alectinib as the first-line therapy,
- TTF of lorlatinib as the second-line therapy,
- TTF of lorlatinib as the third-line or later therapy,
- TTF of lorlatinib across the line of therapy, and
- TTF of subsequent other treatment (e.g., chemotherapy and other TKIs) by each line of lorlatinib therapy

If data allows, Cox proportional hazards model may be performed. Variable selection in Cox proportional hazard model may be performed. Candidates for covariate will be selected by an univariate selection at first. If more than 2 variables are selected in the univariate selection, a stepwise selection will be performed using candidates for covariate after the univariate selection.

7.2.2 Combined TTF

Combined TTF will be summarized using the Kaplan-Meier method. Percentiles of survival curve (25%, median and 75%) with their 2-sided 95% CIs will be estimated. Yearly rates with their 2-sided 95% CI will also be provided. Censor rule is the same as that described in Section 7.2.1.

7.2.3 Objective Response

[figure not shown]
A best overall response (BOR) will be assessed based on reported overall responses at different evaluation time points from each initiation of treatment therapy until discontinuation. An objective response rate (ORR) is defined as the percentage of patients with the BOR of either CR or PR according to RECIST v1.1. Patients without CR or PR will be considered as non-responders.

The ORR will be estimated by dividing the number of patients with BOR of either CR or PR by the number of patients in the FAS. The corresponding exact 2-sided 95% CIs will be provided.

The ORR will be evaluated by each treatment below:

- ORR of alectinib as the first-line therapy,
- ORR of lorlatinib as the second-line therapy, and

PFIZER CONFIDENTIAL

- ORR of lorlatinib as the third-line or later therapy.

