9.1.3. Definition of endpoint

9.1.3.1. TTF and Objective response

TTF is defined as the following:

Endpoint	Start date	Event (whichever occurs earlier)	Censored
TTF	Date of first treatment	Date of any-cause treatment discontinuation including disease progression, treatment toxicity, and death.	Date of last treatment or end of observation period

Objective response is defined as the following:

Complete or partial response as the best adjudication result (complete response [CR] > partial response [PR] > stable disease [SD] > progressive disease [PD], unknown) in a method complies with RECIST version. 1.1 tumor assessment as closely as possible in clinical practice by investigator's judgment.

[figure not shown]

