9.3. Variables

9.3.1. Patient characteristics at baseline

All included cases will be treated with lorlatinib (exposure). Variables for patient characteristics, treatment and outcomes are presented in [Table 1](#)

Variables planned at the baseline will be collected at the time of obtaining the informed consent as much as possible.

Table 1 Key variables of interest and data collection timepoints.

Role	Variable	Timepoint			
		Baseline	Initiation of lorlatinib	Subsequent follow-up visits	End of observation period
Patient characteristics	
 • Age • Sex • Weight • Height • Smoking status (Current smoker, Former smoker, Never smoker) • Brinkman index • ECOG PS (Grades 0 to 5)^a • Date of initial NSCLC diagnosis • Date of advanced NSCLC (TNM stage IIIb-IV) diagnosis • NSCLC histopathological subtype • Clinical NSCLC staging (based on Tumor, Node and Metastasis, TNM)^b • Presence and location of metastasis (including central nervous system, CNS) at initial diagnosis and lorlatinib initiation • Complications/medical history (related to history of treatment for ALK+ NSCLC) • Date of ALK testing • Method of ALK testing • Alectinib initiation date • Alectinib discontinuation date • Presence and location of metastasis (including central nervous system, CNS) during Alectinib treatment • Presence of treatment for some metastasis (including 	X	X	(X) ^c	

PFIZER CONFIDENTIAL

Role	Variable	Timepoint			
		Baseline	Initiation of lorlatinib	Subsequent follow-up visits	End of observation period
	CNS) during Alectinib treatment, and type of treatment(i.e. Radiation Therapy)				
	
 • Reason for alectinib discontinuation • second-line treatment start/end date and drug name, reason for the discontinuation, if lorlatinib is 3rd line treatment 			X	
Treatment	
 • Line for lorlatinib • Lorlatinib initiation date • Dose of lorlatinib • Lorlatinib discontinuation date • Reason for lorlatinib discontinuation • Third-line or later treatment start and end dates, if lorlatinib is second or later line treatment. • Reason for Third-line or later discontinuation, if lorlatinib is second or later line treatment. 		X	X	X ^d

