9.3.3. Objective Response

Definitions of objective response are defined in [Section 9.1.3](#). The following data will be collected: tumor response, and date of tumor response assessment.

Best objective response will be assessed based on reported overall responses at different evaluation time points from each initiation of treatment therapy until discontinuation.

9.3.4. 3rd-line/later line regimen after lorlatinib or pretreatment regimen before lorlatinib treatment

The following 3rd/later-line regimen data will be collected, if lorlatinib treatment is the second line setting: medication, initial date of administration, and reason for discontinuation.

The following second-line regimen data will be collected, if lorlatinib treatment is 3rd/later-line setting: medication, initial date of administration, and reason for discontinuation.

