5.1.3 Objective Response

Objective response (OR) based on an investigator assessment is defined as complete response (CR) or partial response (PR) according to Response Evaluation Criteria in Solid Tumors (RECIST) v1.1 from the first date of interest treatment (either alectinib or lorlatinib) until the date of treatment discontinuation. Repeat assessments were not required to confirm CR and PR due to a nature of real-world clinical setting.

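### Best overall response has no stop at first progression, so a first CR or PR recorded after PD on continued drug counts as a response and could raise the ORR by an unknown, possibly zero, amount

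*SAP*

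**What the plan says.** Three sections define the period over which response is read, and they agree.

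- SAP 7.2.3 takes the responses reported "at different evaluation time points from each initiation of treatment therapy until discontinuation".
- SAP 5.1.3 counts CR or PR "from the first date of interest treatment (either alectinib or lorlatinib) until the date of treatment discontinuation". It adds that no repeat assessment is needed to confirm either.
- Protocol 9.3.3 says: "Best objective response will be assessed based on reported overall responses at different evaluation time points from each initiation of treatment therapy until discontinuation".

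Protocol 9.1.3.1 gives the ranking used to choose among readings: "best adjudication result (complete response [CR] > partial response [PR] > stable disease [SD] > progressive disease [PD], unknown". It places no condition on the order in which the readings occurred. The same section asks for RECIST 1.1 "tumor assessment as closely as possible in clinical practice by investigator's judgment"; the SAP cites RECIST 1.1 without that qualifier.

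Table 1 in protocol 9.3.1 lists "Presence and location of metastasis (including central nervous system, CNS) during Alectinib treatment", and next to it whether such metastases were treated and how, with radiotherapy as the named example. It lists no corresponding items for the lorlatinib period. Protocol 9.3.3 collects tumour response and the date of each assessment.

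**The concern.** The ORR is meant to describe how tumours responded to alectinib and to lorlatinib. A window that closes at discontinuation, combined with a ranking that ignores time order, lets a later reading override a recorded progression. Because confirmation is not required, one such reading is enough.

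The study's own data collection makes the setting plausible for alectinib, since it foresees local treatment of metastases while the drug continues. If PD is recorded, a lesion is treated locally, the drug is continued and a PR is then read, the plan scores a drug response. At stake is whether a published ORR mixes responses seen before progression with readings made after it. In groups of about 20 to 50 patients, one or two such cases change the reported percentage visibly.

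**Working it through.** The documents give no expected ORR, so there is no figure to reproduce. The check has two parts.

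**1. Apply the plan's ranking to example sequences.** The ranking is CR > PR > SD > PD (protocol 9.1.3.1), taken over all readings up to discontinuation (SAP 7.2.3), and then only up to and including the first PD.

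| Readings in time order | BOR as written | BOR with stop at first PD | Responder status changes? |
|---|---|---|---|
| PD, PR | PR | PD | yes |
| SD, PD, PR | PR | SD | yes |
| PR, PD, PR | PR | PR | no |
| PR, PD, CR | CR | PR | no |
| SD, SD, PD | SD | SD | no |

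Only a patient with no CR or PR before PD can change status, and only from non-responder to responder. Relative to a stop at PD, the effect on the ORR is therefore zero or upward.

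**2. Size per affected patient.** Inputs are about 50 patients in total and about 30 in second line (protocol 9.5, SAP 2.1.1), hence 50 − 30 = 20 in later lines. The shift is 100 × 1/N points.

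- Alectinib: 100 × 1/50 = 2.0 points.
- Second-line lorlatinib, denominator 30: 100 × 1/30 = 3.3 points.
- Later-line lorlatinib, denominator 20: 100 × 1/20 = 5.0 points.
- Either lorlatinib group if the FAS denominator in SAP 7.2.3 is taken literally as all 50: 2.0 points.

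**Illustration.** The pre-PD response rate of 40% and the counts of affected patients are assumptions. Intervals are exact (Clopper-Pearson) two-sided 95%.

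| Group | Post-PD responders | ORR | 95% CI |
|---|---|---|---|
| Alectinib, N = 50 | 0 | 20/50 = 40.0% | 26.4–54.8% |
| | 2 | 22/50 = 44.0% | 30.0–58.7% |
| Second-line lorlatinib, N = 30 | 0 | 12/30 = 40.0% | 22.7–59.4% |
| | 1 | 13/30 = 43.3% | 25.5–62.6% |
| | 2 | 14/30 = 46.7% | 28.3–65.7% |
| | 3 | 15/30 = 50.0% | 31.3–68.7% |
| Later-line lorlatinib, N = 20 | 0 | 8/20 = 40.0% | 19.1–63.9% |
| | 1 | 9/20 = 45.0% | 23.1–68.5% |

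Over the full FAS, 12 second-line responders give 12/50 = 24.0% and 14 give 14/50 = 28.0%.

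**The case against.** The strongest reply is that the plan cites RECIST 1.1, so readings after PD may be governed by that standard and need not be spelled out. This does not settle the matter. The plan writes its own window, ending at discontinuation, in three places, and the protocol asks for the standard only as closely as practice allows. A programmer working from SAP 7.2.3 would use the written window. If a stop at PD is intended, the text should say so.

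Several other objections stand and limit the point.

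- The frequency is unknown. The illustrated shifts lie well inside the confidence intervals.
- A reader might infer that the shrinkage in such a patient came from radiotherapy. The documents do not support this. Table 1 does not link local treatment to a recorded PD, to continuation past it or to a later PR, and a later PR could reflect drug effect at other sites.
- Local treatment on drug is documented for alectinib only, where the shift is the smallest, at 2.0 points.
- A reader might also infer that such lorlatinib cases cannot be found afterwards. They can: assessment dates are collected, so a response dated after PD is identifiable. What the listed variables cannot show is whether local treatment preceded it.
- SAP 7.2.3 counts every patient without CR or PR as a non-responder, which pushes the ORR down. The net bias of the reported figure is therefore not known. This does not remove the separate upward effect.
- The ORR is secondary, the study tests no pre-defined hypothesis about it, and protocol 9.9 already discloses that response evaluation may vary between sites.

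**Conclusion.** The point holds in a limited form. The rule as written scores a first CR or PR after PD as a response. That could raise the ORR and cannot lower it compared with a stop at first PD. The amount is unknown and may be zero, because it needs patients who had no earlier response, continued the drug past a recorded PD and were then read as CR or PR. The per-patient shifts rest on the planned group sizes, which the protocol calls flexible, and for lorlatinib also on which denominator is used.

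It would go too far to say that the ORR is inflated: the documents show that the rule permits this, not that it occurs. The consequence is confined to a descriptive secondary estimate. The change is worth making because it is cheap and removes an ambiguity about what a reported response means.

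**What to change.** In SAP 5.1.3, SAP 7.2.3 and protocol 9.3.3, define best overall response over assessments from the start of the treatment to the earliest of:

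- first recorded PD (that assessment included),
- discontinuation of the treatment,
- start of the next systemic therapy.

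Report the until-discontinuation ORR as a sensitivity result, with the number of patients whose status differs between the two. That count replaces the unknown frequency with an observed one. This is an analysis rule only and says nothing about how patients should be treated after progression.

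The cost is a sentence in each section and one date condition in the program; no new data are needed, since assessment dates are already collected. The main ORR may come out slightly lower. The rule does not remove a response read after local treatment when no PD was recorded; for lorlatinib the listed variables would not allow that to be checked.

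Data lock was planned for 30 November 2021 and SAP version 3 is dated 12 May 2022. A change made after lock should be labelled post hoc.

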9.1. Study design

This study is a post-approval, company-sponsored, observational study. This study is a multicenter, non-interventional, retrospective, chart review of patients with ALK+ NSCLC patients treated using lorlatinib as the second/later line therapy in Japan after failure of alectinib treatment as the first line therapy from 20 November 2018.

All decisions regarding clinical management and treatment of the participating patients were made by an investigator as part of standard care in real-world clinical setting and were not contingent upon the patient's participation in the study. Data will be collected if available per study site. Patients in this study are those who started treatment with lorlatinib from 1 May 2019 to 31 December, 2020 in clinical practice..

Observation period : From start date of alectinib to 15 Oct 2021

PFIZER CONFIDENTIAL

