Outcomes	
 • TTF for lorlatinib • TTF for alectinib • If anticancer drug other than lorlatinib is used as 2nd line: TTF of anti-cancer treatment • If anticancer drugs are used after 2nd line lorlatinib: TTF of anti-cancer treatment • Tumor response to lorlatinib based on the RECIST • Tumor response to alectinib and second/3rd line treatment based on the RECIST 			X	X
					X
					(X) ^c

Abbreviations: ECOG PS, Eastern Cooperative Oncology Group Performance Status; CNS, central nervous system; NSCLC, non-small cell lung cancer; ALK, anaplastic lymphoma kinase; TNM, Tumor Node Metastasis; RECIST, Response Evaluation Criteria In Solid Tumors; TTF, time-to-treatment failure.

PFIZER CONFIDENTIAL

^a See Annex 3A for more information.

^b See Annex 3B and C for more information.

^c Not mandatory, but if available.

^dat the date of discontinuation

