4 ANALYSIS SETS/POPULATIONS

4.1 FULL ANALYSIS SET

A full analysis set (FAS) will consist of patients who meet the inclusion criteria and do not meet the exclusion criteria.

PFIZER CONFIDENTIAL

INCLUSION CRITERIA

Patients must meet all of the following inclusion criteria to be eligible for inclusion in the study:

1. Histologically or cytologically confirmed NSCLC, with any TNM stage.
2. Confirmed *ALK* gene rearrangement by any validated tests.
3. Confirmed the treatment with alectinib in the first-line setting as systemic therapy in a medical record.
4. Confirmed the start of treatment with lorlatinib as the second-line or later therapy from 1st May 2019 to 31st December 2020.
5. Availability of clinical information from a medical record.
6. Evidence of a personally signed and dated informed consent document indicating that the patient (or a legally acceptable representative) has been informed of all pertinent aspects of the study.
 - (1) Written consent is not required for patients who were transferred to a hospital, and registration with verbal consent is acceptable.
 - (2) Opt-out enrollment is allowed for patients who have already died.

EXCLUSION CRITERIA

Patients meeting the criterion below will not be included in the study:

1. Participating on any clinical trials of which final results has not yet been reported during the study period.

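### SAP 7.2.3 scores patients with no recorded tumour response as non-responders and plans no count of them, so the ORR cannot separate non-recording from non-response

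*SAP*

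**What the plan says.** SAP 7.2.3 sets the ORR in three steps. Its raw material is what was reported: "A best overall response (BOR) will be assessed based on reported overall responses at different evaluation time points". Patients with CR or PR are then divided "by the number of patients in the FAS". Everyone else is a failure: "Patients without CR or PR will be considered as non-responders". The same rule serves alectinib, second-line lorlatinib and third-line or later lorlatinib, each with an exact 95% CI.

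SAP 4.1 defines the denominator by eligibility: "A full analysis set (FAS) will consist of patients who meet the inclusion criteria and do not meet the exclusion criteria". No inclusion criterion asks for a response assessment.

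The protocol treats response data as possibly incomplete. Section 9.1 says "Data will be collected if available per study site". Section 9.1.3.1 ends its list of response categories with "progressive disease [PD], unknown", so unknown is distinct from SD and PD. In Table 1 (section 9.3.1) one entry in the Outcomes block carries the footnote "Not mandatory, but if available". In the extracted order this mark falls beside tumour response to alectinib and other second- or third-line treatment, while the lorlatinib response row appears to carry a plain X. The table layout is broken, so this reading is probable, not certain.

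SAP section 6 states: "No imputation for missing values will be performed".

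**The concern.** In a trial with mandated scans, an absent assessment often says something about the patient. In a chart review it may only say something about the chart. Under SAP 7.2.3 the two cannot be told apart: the protocol's unknown category does not appear in the SAP, no table of best response is specified, and no assessed-patient or sensitivity analysis is planned. The exact CI covers sampling error only and does not show this uncertainty.

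At stake is how the ORRs can be read. If recording is less complete for alectinib than for lorlatinib, the two ORRs could differ for that reason alone. The literal denominator raises a related problem: the whole FAS, used for a line-specific ORR, would include patients who never received lorlatinib in that line.

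**Working it through.** The plan has no figure to reproduce. Protocol 9.5 calls sample-size and power calculations not relevant, and neither document gives an expected ORR or a rate of missing responses.

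**Inputs from the documents**
- About 50 patients in total, about 30 of them on second-line lorlatinib (Protocol 9.5, SAP 2.1.1); third line or later is 50 − 30 = 20.
- Exact two-sided 95% CIs (SAP 7.2.3), computed here as Clopper-Pearson.

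**Assumptions, not from the documents**
- p, the ORR among patients with a recorded response: 60% (range 40–80%).
- m, the share with none recorded: 20% (range 10–30%).
- q, the true response rate among the unrecorded: from 0 to p.

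**Formulas**
- ORR under SAP 7.2.3 = p(1 − m)
- ORR if every response were known = p(1 − m) + qm
- Error of the SAP rule = −qm, which is never positive
- Error of an assessed-only ORR = p − [p(1 − m) + qm] = (p − q)m, which is positive when q < p

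**Alectinib, N = 50.** Unrecorded: 0.20 × 50 = 10. Responders among the 40 recorded: 0.60 × 40 = 24.
- SAP rule: 24/50 = 48.0% (33.7–62.6)
- Assessed only: 24/40 = 60.0% (43.3–75.1)
- Extremes if none or all of the 10 responded: 24/50 = 48% to 34/50 = 68%

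| q | ORR if all known | Error, SAP rule | Error, assessed only |
|---|---|---|---|
| 60% | 30/50 = 60% | −12 points | 0 |
| 30% | 27/50 = 54% | −6 points | +6 points |
| 0% | 24/50 = 48% | 0 | +12 points |

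With q = p, the error of the SAP rule runs from −4 points (p = 40%, m = 10%) to −24 points (p = 80%, m = 30%).

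**Lorlatinib by line, p = 60%, m = 20%, responders rounded to whole patients**
- Second line, N = 30, 6 unrecorded: 14/30 = 46.7% (28.3–65.7) against 14/24 = 58.3% (36.6–77.9)
- Third line or later, N = 20, 4 unrecorded: 10/20 = 50.0% (27.2–72.8) against 10/16 = 62.5% (35.4–84.8)

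**Literal FAS denominator.** With about 50 in the denominator, second-line lorlatinib ORR could not exceed 30/50 = 60%, nor third-line-or-later ORR 20/50 = 40%. Eighteen second-line responders would be reported as 18/50 = 36.0% (22.9–50.8) instead of 18/30 = 60.0% (40.6–77.3).

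**The case against.** Counting unassessed patients as non-responders is a common, conservative and here pre-specified convention. ORR is a secondary endpoint (Protocol 9.1.2) in a descriptive study, and no comparison of alectinib with lorlatinib ORR is planned. Protocol 9.9 already warns that missing variables may affect accuracy. SAP 7.1 summarises categorical variables by frequency and percentage, which could be taken to cover best response. All of this is fair. It supports keeping the planned ORR, but not leaving it as the only number, since 7.2.3 does not commit to a count of unknowns.

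Four stronger readings are tempting, and the documents do not support them.

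- *Response recording is optional throughout.* The footnote appears to belong to alectinib and other non-lorlatinib treatment. For lorlatinib the concern rests on the general availability statement in Protocol 9.1, which covers every variable.
- *The ORR is biased downward.* The rule's effect is −qm, which is zero if no unrecorded patient responded, for instance after death or progression before a scan. Responses are also unconfirmed and judged by the investigator (SAP 5.1.3), which may push the ORR up, so the net direction of error is not established.
- *The CI would exclude the true rate.* If p = q = 80%, m = 20% and N = 50, then 32/50 = 64% (49.2–77.1) does miss 80%. With 10% unrecorded, 36/50 = 72% (57.5–83.8) includes it. At the lorlatinib line sizes with 20% unrecorded, so do 19/30 = 63.3% (43.9–80.1) and 13/20 = 65.0% (40.8–84.6).
- *SAP 7.2.3 contradicts section 6.* Section 6 is a general rule and 7.2.3 an endpoint definition. No best-response value need be filled in for the definition to work. There is a tension that one sentence resolves, not a contradiction.

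**Conclusion.** The concern holds in a limited form. As written, the only planned ORR merges patients who did not respond with patients whose response was not recorded, and nothing planned lets a reader separate them. The shortfall attributable to the rule is q × m: 12, 6 or 0 points in the N = 50 illustration, depending on q. These sizes rest on assumed values of p, m and q, so they show what is possible and do not estimate what will happen. The case is firmest for alectinib, subject to the broken layout of Table 1, and weaker for lorlatinib. The denominator wording also needs correcting: taken literally, it caps the line-specific lorlatinib ORRs whatever the completeness of recording. For a secondary, descriptive endpoint this is a worthwhile and inexpensive improvement, not a flaw that undermines the study.

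**What to change.** Amend SAP 7.2.3 so that, for each treatment and line, it will:

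1. Tabulate best overall response as CR, PR, SD, PD and unknown.
2. Keep the ORR with unknown counted as non-response, using as denominator the FAS patients who received that treatment in that line, and label it conservative with respect to unrecorded responses.
3. Add, as a sensitivity analysis, the ORR with exact CI among patients with at least one recorded assessment on that treatment, noting that it is too high if unassessed patients respond less often.
4. State that the non-responder rule is an endpoint-specific exception to SAP section 6.

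The cost is a few sentences and one extra column per ORR table. Protocol 9.3.3 already collects tumour response and the assessment date, so no new data are needed. The downside is that the assessed-only ORR may be optimistic, by (p − q)m, which is why it should stand beside the planned ORR and not replace it.

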2.1.1 Study Population

The study population includes Japanese patients with *ALK*⁺ NSCLC who received lorlatinib as the second-line or later therapy after failure of alectinib treatment as the first-line therapy from 20th November 2018.

PFIZER CONFIDENTIAL

The expected number of patients will be approximately 50 patients treated with lorlatinib in total. The number of patients who received lorlatinib as the second-line therapy will be 30 patients, but this should be considered flexible.

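### SAP 7.2.3 divides the second-line and third-line-or-later lorlatinib response rates by the whole FAS (about 50) instead of the patients treated in that line (about 30 and 20), so both rates are understated and their exact CIs are wrong

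*SAP*

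**What the plan says.** SAP 7.2.3 defines the ORR once. It is obtained by "dividing the number of patients with BOR of either CR or PR by the number of patients in the FAS", with exact two-sided 95% CIs, and anyone without a CR or PR is a non-responder. The section then lists three rates to be produced this way: alectinib in first line, "ORR of lorlatinib as the second-line therapy", and lorlatinib in third line or later.

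The FAS is not specific to a line. SAP 4.1 states: "A full analysis set (FAS) will consist of patients who meet the inclusion criteria and do not meet the exclusion criteria". Its fourth inclusion criterion admits lorlatinib starters of either kind: "Confirmed the start of treatment with lorlatinib as the second-line or later therapy from 1st May 2019 to 31st December 2020". The opening of SAP 7 repeats the analysis set: "All analyses described in this section will be conducted using the FAS".

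On size, SAP 2.1.1 says "The expected number of patients will be approximately 50 patients treated with lorlatinib in total" and "The number of patients who received lorlatinib as the second-line therapy will be 30 patients, but this should be considered flexible". Protocol 9.5 gives the same approximate figures.

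**The concern.** Every FAS patient received first-line alectinib, so the FAS denominator is correct for the alectinib ORR. The other two rates each describe only part of the FAS. Patients are classified by the line in which they received lorlatinib, so each belongs to one lorlatinib group and cannot respond in the other. Dividing by the whole FAS adds to each denominator a block of patients who never had the treatment in question and counts them as failures.

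Response to lorlatinib by line is a named secondary endpoint (Protocol 9.1.2), and observed effectiveness of lorlatinib is part of the primary objective (Protocol 8.1). The results are intended for abstracts and publications (Protocol 12). In a descriptive study the estimates and their intervals are the product. Readers will set these rates beside other published response rates and beside each other, and as defined they support neither comparison.

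**Working it through.** The documents state no expected ORR, interval width or power, so there is no figure of the plan's own to reproduce. The check compares the formula as written with the same formula on line-specific denominators.

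**Inputs**

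- FAS size N = 50 (SAP 2.1.1, Protocol 9.5; approximate).
- Second-line lorlatinib n = 30 (same sections; flexible).
- Third line or later n = 50 − 30 = 20 (derived, not stated).
- Exact CI taken as Clopper-Pearson: for x responders out of n, the lower limit is the 2.5% quantile of Beta(x, n − x + 1) and the upper limit is the 97.5% quantile of Beta(x + 1, n − x).
- Responder counts and true response rates are assumptions.

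**Scaling**

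Reported ORR = x/N = (x/n) × (n/N).

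- Second line: 30/50 = 0.60
- Third line or later: 20/50 = 0.40

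These multipliers are also the ceilings if every patient responds: 60% and 40%. With equal true rates in the two lines, the reported rates would differ by a ratio of 0.60/0.40 = 1.5 through group size alone.

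**Point estimates and exact 95% CIs**

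| Group | Line-specific denominator | FAS denominator (as written) |
|---|---|---|
| Second line, 15 responders | 15/30 = 50% (31.3 to 68.7) | 15/50 = 30% (17.9 to 44.6) |
| Second line, 12 responders | 12/30 = 40% (22.7 to 59.4) | 12/50 = 24% (13.1 to 38.2) |
| Third line or later, 8 responders | 8/20 = 40% (19.1 to 63.9) | 8/50 = 16% (7.2 to 29.1) |

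In all three rows the interval as written lies wholly below the correct point estimate.

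**Coverage of the nominal 95% CI**

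For a true rate p in a line with n patients, coverage is the sum, over x = 0 to n, of the Binomial(n, p) probability of x, counting only those x whose interval contains p.

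| True ORR | Second line, denominator 50 | Second line, denominator 30 | Third line or later, denominator 50 | Third line or later, denominator 20 |
|---|---|---|---|---|
| 20% | 74.5% | 98.0% | 37.0% | 97.8% |
| 40% | 42.2% | 96.2% | 2.1% | 96.3% |
| 70% | 0.2% | 97.4% | about 0% | 97.5% |

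**Sensitivity to the split**

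| Second line / third line or later | Multipliers |
|---|---|
| 25 / 25 | 0.50 and 0.50 |
| 30 / 20 | 0.60 and 0.40 |
| 35 / 15 | 0.70 and 0.30 |

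The two multipliers always sum to 1, so the bias can be moved between lines but not removed while both contain patients.

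**The case against.** The strongest reply is that nobody would program it this way. SAP 7 also puts the line-specific TTF curves of 7.2.1 on the FAS, and those can only include patients who started lorlatinib in that line. SAP 2.1.3 sets up second-line and third-line reporting labels, and SAP 4.2 names line of lorlatinib as a subgroup. SAP 5.1.3 counts response from the start of the treatment concerned, which does not exist for a patient who did not have lorlatinib in that line. The FAS sentence may have been meant only to keep patients without a response assessment in the denominator. A total of 50 beside a cohort of about 30 would probably be noticed on the output.

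This bears on how likely the error is to reach a table, not on what the text instructs. None of those sections gives an ORR denominator; SAP 4.2 says only that a subgroup analysis will be considered. A TTF curve restricts itself because it needs a start date. A proportion does not, and here its denominator is spelled out.

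Three further points stand:

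- The endpoint is secondary, no hypothesis is tested on it, and the primary endpoints and the alectinib ORR are unaffected.
- The SAP plans no formal comparison of ORR between lines, so the ratio of 1.5 concerns informal reading.
- A pooled lorlatinib ORR is not required by the protocol endpoint, so its absence is not an error.

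**Conclusion.** The concern holds. SAP 7.2.3 states a rule that gives wrong answers for two of its three response rates, and nothing else in either document corrects it. Followed literally at the planned sizes, it reports 60% of the true second-line ORR and 40% of the true third-line-or-later ORR. At a true rate of 40% in each line, coverage of the nominal 95% intervals falls to about 42% and 2%.

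The multipliers rest on the planned 50 and 30, which the documents call approximate or flexible, and on 20 by subtraction. The responder counts and true rates are illustrative. The direction does not depend on them: both rates are understated whenever both lines contain patients. The damage is confined to descriptive secondary estimates, but it should be corrected before any of them is reported.

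**What to change.** Replace the denominator sentence in SAP 7.2.3 with wording such as:

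> Each ORR is the number of patients with a best overall response of CR or PR to the treatment in the stated line, divided by the number of FAS patients who received that treatment in that line. Patients in that denominator without a response assessment are counted as non-responders. Exact (Clopper-Pearson) two-sided 95% CIs use the same denominator.

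This leaves the full FAS for alectinib, the second-line lorlatinib patients for the second-line rate, and the third-line-or-later lorlatinib patients for the other. The tables should print the denominator beside each rate.

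As an option, add lorlatinib ORR across all lines, for which the full FAS is correct; SAP 7.2.1 already does the equivalent for TTF.

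The cost is one SAP sentence and a change of denominator in the program. Line of lorlatinib is already collected (Protocol Table 1), so no new data are needed. SAP version 3 (12 May 2022) is later than the planned completion of analysis (31 December 2021, Protocol 6), so any ORR tables already produced should be checked against the corrected definition.
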